4.4.7 Removal of Subjects from Therapy or Assessment

4.4.10.1 Reasons for Removal of Subjects from Therapy or Assessment

Each subject has the right to withdraw from study treatment at any time. In addition, the investigator may discontinue a subject from the study treatment at any time for any reason if the investigator considers it necessary, including the occurrence of an adverse event or noncompliance with the protocol. Each subject will be withdrawn from the study if any of the following occur:

- 1) The subject experiences either clinical or radiographic progressive disease.
- 2) The subject requires other radiotherapy or alternate antineoplastic agents during the study period.
- 3) The investigator believes it is in the best interest of the subject.
- 4) Clinically significant deterioration of the subject's medical status as determined by the investigator.
- 5) Subject becomes pregnant or begins breastfeeding during the treatment portion of the study.
- 6) The subject or subject's legally acceptable representative decides to withdraw consent for any reason.
- 7) Any other medical reason that the study investigator deems appropriate.

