4.4.10.2 Discontinuation of Individual Subjects

When a subject discontinuation from the study (without reaching a protocol-defined endpoint) is planned, the investigator will notify the PI as soon as possible (provided, in each case, subject care and safety are not compromised). When a subject discontinues the study, a final visit will be conducted (preferably prior to the initiation of another anticancer therapy). However, these procedures should not interfere with the initiation of any new treatments or therapeutic modalities that the investigator feels are necessary to treat the subject's condition. Following discontinuation of the study drug, the subject will be treated in accordance with the investigator's best clinical judgment. At the final visit, the reason(s) for the discontinuation from the study will be recorded and a physical examination, body weight, vital signs measurement, laboratory analyses, performance status, tumor assessment, and an assessment of adverse events will be performed as soon as possible after discontinuation from the study. All subjects will have one final visit, which does not need to be performed for subjects who have had a visit greater than 30 days after discontinuation of the study drugs. If a subject is discontinued from the study with an ongoing adverse event or an unresolved clinically significant laboratory result, personnel will attempt to provide follow-up until a satisfactory clinical resolution of the laboratory result or adverse event is achieved. In the event that a positive result is obtained on a pregnancy test for a subject during the study, the administration of study drug to that subject must be discontinued immediately.

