8.2.1 Median recurrence-free survival (mPFS)

8.2.2 Median overall survival (mOS)

8.3 Primary Endpoint:

The primary endpoint is to determine the RP2D between the 2 proposed schedules. Using a 3+3 dose-escalation schema, 2-12 patients will be required to determine the RP2D.

Co-primary endpoints:

8.3.1 Safety: adverse event data will be collected and presented as descriptive statistics using the CTCAE version 5.0.

8.3.2 Feasibility: we will track the success rate in screening patients, completion of proton beam planning, completion of proton beam treatment, and completion of adjuvant therapy (including number of cycles completed and relative dose intensity).

8.4 Exploratory Endpoints:

8.4.1 Recurrence-free survival (RFS), defined as time from surgery until evidence of disease recurrence.

8.4.2 Overall survival (OS), defined as time from surgery until death from any cause or last follow-up.

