8.6 Analytic plan for exploratory objectives

8.6.1 The nonparametric Kaplan-Meier method will be used to estimate median RFS.

8.6.2 The nonparametric Kaplan-Meier method will be used to estimate median OS.

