8.7 Safety Assessments

8.7.1 The safety of FFX and PRT will be assessed by evaluating study drug exposure, adverse events, serious adverse events, oncology-related events, all deaths, as well as changes in laboratory determinations and vital sign parameters.

8.7.2 A summarization of the number of days and/or cycles subjects were exposed to FFX and PRT will be provided.

8.7.3 Analyses of adverse events (and serious adverse events) will include only "treatment-emergent" events, *i.e.*, those that have an onset on or after the day of the first dose of study drug. Analyses will not include those that have an onset greater than 30 days after the treatment. Treatment emergent adverse events will be summarized by system organ class and preferred term according to the MedDRA adverse event coding dictionary. The percentage of subjects experiencing an adverse event at a given severity, NCI CTCAE toxicity grade, and relationship to study drug will be provided.

8.7.4 The number of subject deaths will be summarized (1) for deaths occurring while the subject was still receiving study drug in this study, (2) for deaths occurring off treatment within 30 days after the last dose of study drug, and (3) for all deaths in this study regardless of the number of days after the last dose of study drug. The relatedness of the deaths to the study drugs will also be provided.

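### The withdrawal rule conflicts with the overall-survival plan: applied literally, survival follow-up ends at about recurrence and the exploratory OS curve is too high

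*Combined protocol and SAP*

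**What the plan says.** Section 4.4.10.1 carries the heading "Reasons for Removal of Subjects from Therapy or Assessment". It begins with stopping study treatment, which patient or investigator may do at any time. It then changes its object: "Each subject will be withdrawn from the study if any of the following occur". The first reason is "The subject experiences either clinical or radiographic progressive disease", and the second is "The subject requires other radiotherapy or alternate antineoplastic agents during the study period".

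Section 4.4.10.2 adds "All subjects will have one final visit", preferably before new anticancer therapy, and waives it for anyone already seen more than 30 days after stopping the study drugs. The only later contact it describes is for an ongoing adverse event or an unresolved, clinically significant laboratory result.

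On the outcome side:

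- Section 8.4.2 (and 2.4.2): "Overall survival (OS), defined as time from surgery until death from any cause or last follow-up".
- Section 8.6.2: "The nonparametric Kaplan-Meier method will be used to estimate median OS". No censoring rule is given.
- Tables 2 and 3 have a survival row marked at the follow-up visits, every 3 months up to 24 months. Table 4 lists the same item under end of treatment and follow-up.
- Section 8.7.4 plans three death counts. The third is "for all deaths in this study regardless of the number of days after the last dose of study drug".

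**The concern.** In resected pancreatic cancer, most deaths can be expected to follow a recurrence. If a patient leaves the study at recurrence and is not contacted again, the last follow-up date in the OS definition falls at about the recurrence date. The patient is then censored just as the risk of death rises. Kaplan-Meier assumes that censored patients have the same later risk as those still followed, and here they would not. The OS curve would mainly count deaths without recurrence, and the third death count in 8.7.4 would be short.

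Median OS is a stated exploratory objective, and the synopsis says the trial is to inform later designs. An inflated curve would therefore be carried forward.

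**Working it through.** **1. The passages side by side.** One paragraph of 4.4.10.1 uses both study treatment and study, so leaving the study is the literal reading of the withdrawal rule. No section says that vital status is collected after withdrawal. Equally, no section says that OS is censored at recurrence or that withdrawn patients are excluded from the three-monthly survival item. The documents therefore conflict, and the loss of deaths is conditional on how the conflict is resolved.

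**2. The plan's own figure.** No event count, precision target or OS assumption is given. The only size figure is that of the 3+3 design. Enumerating its rules by full cohorts gives totals of 3, 6, 9 or 12, which confirms the stated maximum of 12. N = 12 is used below.

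**3. Length of follow-up from surgery.** Assumptions: 4 to 12 weeks from surgery to cycle 1, and the 24 months counted from end of treatment (day 1 of cycle 12). Cycle 6 adds 7 days (DL2) or 14 days (DL1).

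- Shortest: (28 + 11 × 14 + 7) / 30.44 = 6.2 months; + 24 = 30.2 months.
- Longest: (84 + 11 × 14 + 14) / 30.44 = 8.3 months; + 24 = 32.3 months.

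**4. Model.** There are three states (recurrence-free, recurred, dead) with constant hazards from surgery. Let λ = ln 2 / (median time to recurrence or death), f = share of first events that are deaths without recurrence, h0 = fλ, h1 = λ − h0, and m = hazard of death after recurrence.

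- Complete follow-up: S(t) = exp(−λt) + [h1 / (λ − m)] × [exp(−mt) − exp(−λt)].
- Censored at recurrence, Kaplan-Meier tends to exp(−h0·t).

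For each scenario m is set so that S(54.4) = 0.5, where 54.4 months is the FFX median cited in sections 1.2 and 1.8. The documents give neither the time to first event nor f, so both are varied: 12, 20 or 30 months, and 0 to 20%. The model does not condition on being recurrence-free at cycle 6.

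**5. Worked case (20 months, f = 5%).** λ = 0.6931 / 20 = 0.03466 and h0 = 0.00173. Calibration gives a median survival after recurrence of 26.8 months.

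- Apparent S(24) = exp(−0.00173 × 24) = 0.96; with complete follow-up 0.82.
- Deaths by month 32: 12 × (1 − 0.731) = 3.2. Deaths counted: 12 × 0.05 × [1 − exp(−0.03466 × 32)] = 0.4.

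| Median to first event (months) | f | S(24) complete | S(24) censored at recurrence | Gap | Deaths of 12 by month 32: true / counted |
|---|---|---|---|---|---|
| 12 | 0% | 0.818 | 1.000 | 0.18 | 3.26 / 0.00 |
| 12 | 20% | 0.744 | 0.758 | 0.01 | 3.94 / 2.02 |
| 20 | 5% | 0.818 | 0.959 | 0.14 | 3.23 / 0.40 |
| 30 | 0% | 0.826 | 1.000 | 0.17 | 3.17 / 0.00 |
| 30 | 20% | 0.798 | 0.895 | 0.10 | 3.41 / 1.25 |

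The bias is upward whenever m exceeds h0. The 0.01 row is an edge case where recurrence hardly raises the hazard of death: m = ln 2 / 51.6 = 0.0134 a month against h0 = 0.2 × ln 2 / 12 = 0.0116.

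**6. The median.** In 20,000 simulated trials of 12 patients under the worked case, followed to month 32, the Kaplan-Meier median was reached in about 8% with complete follow-up and 0.4% with censoring at recurrence.

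**The case against.** The best defence is that the protocol plainly means to capture deaths. OS counts death from any cause, the survival item stands in the follow-up column without restriction to recurrence-free patients, and 8.7.4 asks for all deaths whatever the interval from the last dose. The document also uses its terms loosely: 4.4.10.2 moves between leaving the study and stopping the study drug. On that view 4.4.10.1 is careless wording, and the site would go on recording deaths.

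Much of this stands. A reader might infer that deaths after recurrence are certain to be lost. The documents do not support that; it follows only if the withdrawal rule is applied as written. What the defence does not supply is a procedure. The survival item belongs to clinic visits with scans and blood work, no survival-only contact is described, and 8.7.4 speaks of deaths in the study, which a withdrawn patient has left.

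A reader might also infer that this rule is what defeats the median OS objective. It is not the main cause: 30 to 32 months of follow-up is short against a 54.4-month benchmark, with or without the rule.

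A larger bias can be produced with harsher inputs. Take entry 4 months after surgery, median recurrence 12 months later, median survival after recurrence 10 months and other deaths at 1% a year. Apparent 24-month OS is then about 98% against a true 63%. But this puts 6.5 of 12 patients dead by month 32, a median below 32 months and so worse than the 35.0 months cited for gemcitabine alone. The apparent 98% also follows directly from the assumed 1% a year.

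**Conclusion.** The concern holds as a conflict with a conditional consequence. The withdrawal and final-visit text cannot be followed literally while also delivering OS to death from any cause and a count of all deaths. If it is followed literally, OS is censored informatively at about recurrence. Under the scenarios above, 24-month OS is then overstated by about 0.01 to 0.18, and of roughly 3.1 to 3.9 deaths among 12 patients by month 32 only 0 to 2.0 are counted. These figures rest on constant hazards, the 54.4-month scaling and assumed recurrence patterns.

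Severity is minor. OS is exploratory, there are at most 12 patients, there is no comparator, and the RP2D rule uses DLTs only.

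**What to change.** Reconcile 4.4.10.1 and 4.4.10.2 with 8.4.2, 8.6.2, 8.7.4 and Tables 2 to 4 by adding three statements:

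1. Withdrawal under 4.4.10.1, for any reason other than withdrawal of consent, does not end survival follow-up.
2. For these patients vital status is collected by phone or chart on the existing three-monthly schedule to 24 months.
3. Patients not known to have died are censored for OS at the date last known alive, not at recurrence or at the final visit.

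The rules for stopping treatment and for pregnancy should stay as they are. Rewording the pregnancy reason in 4.4.10.1 as a treatment stop only would set it against section 6.6, which requires leaving the study. Section 6.6 already collects information after that point, so a vital-status check is compatible with it.

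The cost is a few sentences in an amendment and a short phone or chart check for at most 12 patients. It should be made before patients recur and contact is lost. It will not make median OS estimable within the planned follow-up; it makes the curve and the death count correct as far as they go.

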4.4.10.2 Discontinuation of Individual Subjects

When a subject discontinuation from the study (without reaching a protocol-defined endpoint) is planned, the investigator will notify the PI as soon as possible (provided, in each case, subject care and safety are not compromised). When a subject discontinues the study, a final visit will be conducted (preferably prior to the initiation of another anticancer therapy). However, these procedures should not interfere with the initiation of any new treatments or therapeutic modalities that the investigator feels are necessary to treat the subject's condition. Following discontinuation of the study drug, the subject will be treated in accordance with the investigator's best clinical judgment. At the final visit, the reason(s) for the discontinuation from the study will be recorded and a physical examination, body weight, vital signs measurement, laboratory analyses, performance status, tumor assessment, and an assessment of adverse events will be performed as soon as possible after discontinuation from the study. All subjects will have one final visit, which does not need to be performed for subjects who have had a visit greater than 30 days after discontinuation of the study drugs. If a subject is discontinued from the study with an ongoing adverse event or an unresolved clinically significant laboratory result, personnel will attempt to provide follow-up until a satisfactory clinical resolution of the laboratory result or adverse event is achieved. In the event that a positive result is obtained on a pregnancy test for a subject during the study, the administration of study drug to that subject must be discontinued immediately.

4.4.10.3 Discontinuation of Entire Study

The investigators may terminate this study provided that written notice is submitted at a reasonable time in advance of the intended termination. The following procedures for discontinuation will be followed:

- 1) If the investigators have decided to prematurely discontinue the study, the investigators will promptly notify in writing the IRB of the decision and give detailed reasons for the discontinuation.
- 2) The PI must promptly notify enrolled subjects of the premature discontinuation and administer appropriate treatments such as replacement of protocol therapy by other appropriate regimens.

4.4.8 Protocol Deviations

The investigator should not implement any deviation from the protocol without prior review and agreement by the Sponsor and in accordance with the IRB and local regulations, except when necessary to eliminate an immediate hazard to study subjects.

Table 2. Study Activities – Dose Level 1

	Screening ^a	C6D1 ^b	C6D2	C6D3	C6D15	C6D16	C6D17	C6D18	C6D19	D1 of C7 ^c -C12	EOT ^d	F/U ^e
Informed Consent	X											
Demographics	X											
Medical History	X											
ECOG PS ^f	X	X			X					X	X	X
Concomitant Medications Collection	X	X			X					X	X	X
Adverse Events Assessment	X	X			X					X	X	X
Vital Signs	X	X			X					X	X	X
Height	X	X										
Weight	X	X			X					X	X	X
History and Physical Exam	X	X			X					X	X	X
CT or MRI Scan Tumor Evaluation and Assessment ^g	X										X ^h	X
β-hCG ⁱ	X	X										
CBC with differential	X	X			X					X	X	X
CMP ^j	X	X			X					X	X	X
PT/INR and aPTT	X											
CA19-9	X	X								X	X	X
mFOLFIRINOX		X	X	X						X		
Proton Beam Planning	X											
Proton Beam Therapy					X	X	X	X	X			
Survival		X			X					X	X	X

^aScreening visit must occur within 28 days of C6D1 of mFOLFIRINOX

^bThis assumes proton therapy will be administered during C6 (may be delivered during C6-C11 if necessary)

^cC6 is a 28 day cycle in dose level 1 (C7D1 = C6D29), all other cycles are 14 days in length

^dEnd of treatment (D1 of last cycle of mFOLFIRINOX, typically C12)

^eFollow-up assessments will be performed every 3 months for up to 24 months

^fEastern Cooperative Oncology Group Performance Status

^gScreening scans should be done within 2 months of C6D1

^hCan be performed within 14 days of the EOT visit

ⁱSerum (screening) and urine (C6D1) pregnancy tests (for women of childbearing potential only)

^jComprehensive metabolic panel: sodium, potassium, chloride, bicarbonate, BUN, creatinine, glucose, calcium, AST, ALT, alkaline phosphatase, total bilirubin, total protein, and albumin

Table 3. Study Activities – Dose Level 2

	Screening ^a	C6D1 ^b	C6D2	C6D3	C6D8	C6D9	C6D10	C6D11	C6D12	D1 of C7 ^c -C12	EOT ^d	F/U ^e
Informed Consent	X											
Demographics	X											
Medical History	X											
ECOG PS ^f	X	X			X					X	X	X
Concomitant Medications Collection	X	X			X					X	X	X
Adverse Events Assessment	X	X			X					X	X	X
Vital Signs	X	X			X					X	X	X
Height	X	X										
Weight	X	X			X					X	X	X
History and Physical Exam	X	X			X					X	X	X
CT or MRI Scan Tumor Evaluation and Assessment ^g	X										X ^h	X
β-hCG ⁱ	X	X										
CBC with differential	X	X			X					X	X	X
CMP ^j	X	X			X					X	X	X
PT/INR and aPTT	X											
CA19-9	X	X								X	X	X
mFOLFIRINOX		X	X	X						X		
Proton Beam Planning												
Proton Beam Therapy	X				X	X	X	X	X			
Survival		X			X					X	X	X

^aScreening visit must occur within 28 days of C6D1 of mFOLFIRINOX

^bThis assumes proton therapy will be administered during C6 (may be delivered during C6-C11 if necessary)

^cC6 is a 21 day cycle in dose level 1 (C7D1 = C6D15), all other cycles are 14 days in length

^dEnd of treatment (D1 of last cycle of mFOLFIRINOX, typically C12)

^eFollow-up assessments will be performed every 3 months for up to 24 months

^fEastern Cooperative Oncology Group Performance Status

^gScreening scans should be done within 2 months of C6D1

^hCan be performed within 14 days of the EOT visit

ⁱSerum (screening) and urine (C6D1) pregnancy tests (for women of childbearing potential only)

^jComprehensive metabolic panel: sodium, potassium, chloride, bicarbonate, BUN, creatinine, glucose, calcium, AST, ALT, alkaline phosphatase, total bilirubin, total protein, and albumin

Table 4. Study Activities Checklist

Screening

Informed Consent	_____
Demographics	_____
Medical History	_____
ECOG PS	_____
Concomitant Medications Collection	_____
Adverse Events Assessment	_____
Vital Signs	_____
Height	_____
Weight	_____
History and Physical Exam	_____
CT or MRI Scan	_____
Tumor Evaluation and Assessment	_____
β-hCG	_____
CBC with Differential	_____
Comprehensive Metabolic Panel	_____
PT/INR and aPTT	_____
CA19-9	_____
Proton Beam Planning	_____

Cycle 6 Day 1

ECOG PS	_____
Concomitant Medications Collection	_____
Adverse Events Assessment	_____
Vital Signs	_____
Height	_____
Weight	_____
History and Physical Exam	_____
β-hCG	_____
CBC with Differential	_____
Comprehensive Metabolic Panel	_____
CA19-9	_____
mFOLFIRINOX (Days 1-3)	_____
Survival	_____

Cycle 6 Day 15 (Dose Level 1) or Cycle 6 Day 8 (Dose Level 2)

ECOG PS	_____
Concomitant Medications Collection	_____
Adverse Events Assessment	_____
Vital Signs	_____
Weight	_____
History and Physical Exam	_____
CBC with Differential	_____
Comprehensive Metabolic Panel	_____
Proton Beam Therapy (Days 15-19 in Dose Level 1, Days 8-12 in Dose Level 2)	_____
Survival	_____

Day 1 of Subsequent Cycles (7-12)

ECOG PS	_____
---------	-------

Concomitant Medications Collection _____
Adverse Events Assessment _____
Vital Signs _____
Height _____
Weight _____
History and Physical Exam _____
CBC with Differential _____
Comprehensive Metabolic Panel _____
CA19-9 _____
mFOLFIRINOX (Days 1-3) _____
Survival _____

End of Treatment

ECOG PS _____
Concomitant Medications Collection _____
Adverse Events Assessment _____
Vital Signs _____
Height _____
Weight _____
History and Physical Exam _____
CBC with Differential _____
Comprehensive Metabolic Panel _____
CA19-9 _____
Survival _____

Follow-Up

ECOG PS _____
Concomitant Medications Collection _____
Adverse Events Assessment _____
Vital Signs _____
Height _____
Weight _____
History and Physical Exam _____
CBC with Differential _____
Comprehensive Metabolic Panel _____
CA19-9 _____
Survival _____

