4.4 Detailed Patient Assessments

Subject assessments (physical examinations, vital signs, performance status, chemistry, hematology, medication review, and adverse event evaluations) will be conducted at screening, C6D1, C6D15 (DL1) or C6D8 (DL2), and D1 of every subsequent cycle (every 14 days \pm 3 days). Details are provided in Tables 2 and 3, and a checklist highlighting the important events for screening through the completion of the trial is provided below in Table 4. Patients will meet with the radiation oncologist during screening (prior to C6D1), during PRT, and at follow-up visits as outlined below.

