4.4.6 Imaging and Evaluation

Patients will undergo a baseline tumor evaluation with imaging studies within 28 days prior to C6D1. Imaging studies should include a diagnostic CT scan of the chest, abdomen, and pelvis with PO and IV contrast (unless medically contraindicated). If a patient has an allergy to IV contrast, appropriate pre-medication can be given to prevent a contrast reaction. Patients may undergo other modalities such as an MRI instead of a CT scan at the treating physician's discretion if appropriate (such as severe allergy to CT contrast, extremity tumors, bone metastases requiring bone scans, etc.).

The first follow-up surveillance scan will occur within 14 days of the End of Treatment (EOT) visit which will be scheduled following completion of C12 or the last cycle of FFX administered. Follow-up visits including scans (CT or MRI) and blood work including CA19-9 will then occur every 3 months up to 24 months.

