5.0 DOSAGES AND DISPENSATION OF DRUGS

5.1 FFX Administration

The study drugs are defined as 5-FU, LV, oxaliplatin, and irinotecan (FFX). Due to the infusional 5-FU, study drugs must be administered via central line (mediport, PICC, or other). Treatment cycles are every 14 days \pm 3 days (except for C6 which is 28 days in DL1 and 21 days in DL2). The study drug dosages and administration are only recommended – dosages and supportive medication can be modified at the discretion of the investigator, taking into consideration dose modifications during cycles 1-5. Per the PRODIGE 24 trial, the 5-FU bolus is omitted and irinotecan is 150 mg/m². A research infusion nurse will access the patient's line. Treatment will then be administered in the following order (substitutions for prophylactic medications are allowed at the treating investigator's discretion):

Table 5. Drug Administration

Drug	Indication	Dose/Route	Duration
Fosaprepitant	Nausea prophylaxis	150 mg IV	30 minutes
Ondansetron	Nausea prophylaxis	16 mg IV	15 minutes
Dexamethasone	Nausea prophylaxis	10 mg IV	15 minutes
Leucovorin	Treatment	400 mg/m ² IV	60 minutes
Oxaliplatin	Treatment	85 mg/m ² IV	120 minutes (can be administered simultaneously with leucovorin via a Y-connector)
Atropine	Diarrhea prophylaxis	0.5 mg IV	IV push
Irinotecan	Treatment	150 mg/m ² IV	90 minutes
5-fluorouracil	Treatment	2400 mg/m ² IV	46 hours (continuous infusion)
Pegfilgrastim on-pro	Growth factor support	6 mg SC	Administered on day 3 (after 5-fluorouracil pump is unhooked)

The patient will return to the research infusion clinic after 46 hours for disconnection of the 5-FU infusional pump and administration of pegfilgrastim on-pro. Use of growth factor support is highly recommended but is at the discretion of the investigator. Alternatively, pegfilgrastim 6 mg SC can be administered on day 4 (if not using on-pro administration).

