6.4 Adverse Event Collection Period

All adverse events reported from the time of study drug administration until 30 days following discontinuation of study drug administration have elapsed will be collected, whether elicited or spontaneously reported by the subject. In addition, serious adverse events will be collected from the time the subject signed the study-specific informed consent.

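### The end-of-treatment visit is on day 1 of the last FFX cycle in Tables 2 and 3 but after that cycle in section 4.4.6; as tabled, no assessment follows last-cycle dosing inside the 30-day AE window

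*Combined protocol and SAP*

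**What the plan says.** **Schedule tables.** Footnote d, identical in Tables 2 and 3, defines EOT as the end "of treatment (D1 of last cycle of mFOLFIRINOX, typically C12". The tables mark AE assessment, vital signs, CBC and CMP on day 1 of C7 to C12, at EOT and at follow-up. Footnote e says that follow-up "assessments will be performed every 3 months for up to 24 months".

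**Section 4.4.6.** This refers to an EOT "visit which will be scheduled following completion of C12 or the last cycle of FFX administered". The first surveillance scan is to be within 14 days of that visit, and the 3-monthly follow-up comes after it.

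**Section 4.4.** Assessments on treatment are at screening, C6D1, the first PRT day "and D1 of every subsequent cycle (every 14 days", with a 3-day tolerance. No later assessment is tabled within C7 to C12.

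**Sections 6.4 and 8.7.3.** AEs from study drug administration "until 30 days following discontinuation of study drug administration have elapsed will be collected". On analysis, 8.7.3 says: "Analyses will not include those that have an onset greater than 30 days after the treatment". Section 5.1 defines study drug as the four FFX agents.

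**Section 4.4.10.2.** Every subject is to have one final visit, which includes an AE assessment, laboratory tests and vital signs. It is timed from discontinuation from the study and is not needed if a visit took place more than 30 days after study drug stopped.

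**The concern.** The two EOT definitions lie on opposite sides of the last cycle's exposure. On day 1 of a cycle, a patient is assessed for the toxicity of the cycle before. For every earlier cycle, the next day-1 visit picks up that toxicity about 14 days later. For the last cycle, EOT is the only tabled visit that could do so before the first follow-up visit. If EOT is placed on C12D1, it repeats a visit that the tables already contain and adds nothing after dosing.

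Safety, as descriptive CTCAE data, is a co-primary endpoint (sections 2.3.1 and 8.3.1). Asymptomatic laboratory toxicity in the last cycle, such as cytopenia or raised transaminases, would be seen only if someone ordered an unscheduled test. In a study of at most 12 evaluable patients, a few missed laboratory grades would show in the summary percentages.

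There is also a practical problem. For a patient who stops FFX early, the last cycle is known to be the last only after its day 1 has passed. An EOT visit on that day cannot be scheduled in advance.

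**Working it through.** The plan states no figure to reproduce. The check is visit-day arithmetic on the plan's own schedule, with C12D1 as day 1. It is the same for both dose levels.

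**Inputs**
- Last FFX exposure: section 5.1 says "The patient will return to the research infusion clinic after 46 hours for disconnection of the 5-FU infusional pump", so dosing ends on day 3.
- AE window: 30 days after study drug stops (section 6.4).
- First follow-up: 3 months after EOT. Assumptions: follow-up is counted from EOT, and a month is 28 to 31 days. Footnote e names no anchor.

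**EOT as in footnote d (C12D1)**
- AE window closes: 3 + 30 = C12D33.
- First follow-up: 1 + 3 × 28 = C12D85, to 1 + 3 × 31 = C12D94.
- Days after last dose: 85 − 3 = 82, to 94 − 3 = 91.
- Days after the window closes: 85 − 33 = 52, to 94 − 33 = 61.
- Gap between tabled assessments: 84 to 93 days, against 14 days between earlier day-1 visits.
- Tabled AE, vital-sign, CBC or CMP assessments after C12D1 and up to C12D33: none.

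Sensitivity to the anchor: if follow-up is counted from a scan up to 14 days either side of EOT, the first visit falls 52 − 14 = 38 to 61 + 14 = 75 days after the window closes. It is outside the window in every case.

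**EOT as in section 4.4.6 (after the last cycle)**
- A 14-day cycle is complete at about C12D15, or C12D12 to D18 if the 3-day tolerance is assumed to apply.
- Days after last dose: 12 − 3 = 9, to 18 − 3 = 15. This is inside the window.
- Section 4.4.6 sets no latest day, so the visit is inside the window only if held by C12D33.

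**Which definition the rest of the schedule fits.** In Tables 2 and 3 the day-1 column for C7 to C12 carries an mFOLFIRINOX mark and the EOT column does not. Table 4 lists End of Treatment as its own block without an mFOLFIRINOX line. The layout treats EOT as a separate, non-dosing visit, as section 4.4.6 does.

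**Does the final visit close the gap?** It has no fixed day and does not appear in Tables 2 to 4. The first follow-up visit, 82 to 91 days after the last dose, itself meets the waiver condition. A patient could therefore comply fully and still have no assessment in the window.

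**DLT window (28 days from first PRT dose, section 6.9)**
- PRT in C6. DL1: C6D15 + 28 = C6D43 = C7D15, which is C8D1. DL2: C6D8 + 28 = C6D36 = C7D15, again C8D1. If C7 and C8 are given, both have tabled assessments, so EOT timing is irrelevant.
- PRT in C11 (allowed by footnote b), assuming C11 is extended as C6 is. C12D1 is 29 − 15 = 14 days after first PRT in DL1 and 22 − 8 = 14 days in DL2. The window ends at C12D15 in both, so its second half has no tabled assessment after C12D1.
- FFX stopped after C6. Footnote d dates EOT to C6D1, which is 14 days (DL1) or 7 days (DL2) before the first PRT dose. The last tabled assessment before follow-up is then the first PRT day.

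**The case against.** The best reply is that footnote d is a slip. Section 4.4.6, the table layout and the checklist all point to a visit after the last cycle, and on that reading the gap largely disappears. This stands as to what was probably intended. It does not remove the problem, because the footnote is the operative definition in the tables that staff work from.

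Several stronger readings are tempting, and the documents do not support them.

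- *Patients who complete treatment have no final visit.* Section 4.4.10.2 gives one to all subjects. What holds is that the visit is undated, untabled and waivable.
- *Last-cycle toxicity is not captured.* Section 6.4 collects elicited and spontaneous AEs to 30 days, section 6.1 requires routine monitoring, SAEs are reported within 24 hours, and a later visit can record earlier onsets. Only scheduled and laboratory ascertainment is lost.
- *The 30-day exclusion in 8.7.3 causes the loss.* That rule works by onset date and excludes the same events under either EOT definition.
- *The completion-of-therapy endpoint is affected.* Cycles completed and relative dose intensity come from dosing records.
- *The loss is greatest in patients who stop for toxicity.* This is not shown. Those who leave the study are to have their final visit as soon as possible. The gap concerns patients who stop or complete FFX and stay in follow-up.

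**Conclusion.** The contradiction between footnote d and section 4.4.6 is real, and the two must be reconciled. If the tables are followed, the last FFX cycle has no tabled AE, vital-sign, CBC or CMP assessment between its dosing and the close of the AE window at about C12D33. The next tabled visit is then roughly 52 to 61 days after that close. Those figures rest on counting follow-up from EOT and on months of 28 to 31 days. The absence of a tabled assessment in the window does not depend on the month length, or on whether follow-up runs from EOT or from the EOT scan.

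The effect is on how completely the co-primary safety summary covers one cycle per patient. A reader might infer that the RP2D decision is at risk. With PRT in C6 and FFX continuing, it is not. The DLT window is touched only when FFX stops soon after PRT or when PRT is given late. The EOT scan date would also move by about two weeks, which bears only on an exploratory RFS estimate.

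**What to change.** Amend footnote d in both Table 2 and Table 3 to the section 4.4.6 definition: EOT takes place after completion of the last FFX cycle given. Add, there and in 4.4.6, that the visit falls within the protocol's own 30-day AE window after the last FFX dose, since 4.4.6 now sets no latest day. Tie the EOT scan to that visit, keeping the existing 14-day allowance.

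The cost is two footnotes and one clause in 4.4.6. Where EOT would have been merged with C12D1, it also means one attendance per patient, at a visit that the tables and checklist already list separately. No change to treatment is involved.
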